## Project Timeline

Study Activities	Year 1	Year 2	Year 3	Year 4	Year 5
Project Preparation					
Aim 1: Recruitment					
Aim 1: Qualitative interview					
Aim 1: analysis of qualitative data and preparation for					
Aim 2: Community Health Worker /staff training					
Aim 2: MILS Intervention material preparation					
Aim 2: Recruitment and pre-intervention assessment					
Aim 2: MILS Intervention implementation					
Aim 2: Post-intervention assessment					
Aim 2: 6 Month Post-intervention assessment					
Aim 2: Wait-list social media					
Aim 2: Analysis of the Effectiveness of MILS					
Aim 3: Recruitment					
Aim 3: Qualitative participant feedback on MILS					
Aim 3: Analysis of qualitative data					
Community feedback					
Project report					
Conferences, manuscripts					
Disseminate MILS					

**\*\*Year 1 highlighted in blue**

## Study Methods

### Procedure

**Objective 1:** The research assistant (RA) is in charge of the patient schedule (list provided by the Radiology department and sends the schedule to UMC to reserve the patient room before the interview. The R.A. contacts the patient and confirms he/she will attend the interview. Eligible participants will be approached in the clinic by staff recruiters. The recruiter will briefly explain the study. If the participant is interested, they will meet with a research assistant (RA) in a private room to learn more about the study and will be provided with an information sheet on the details of the study and complete the interview. R.A.s will be trained to recruit, consent and conduct interviews for the proposed study. During the interviews, the project coordinator will follow a semi-structured interview guide with a list of questions to ask participants to share their personal perspectives and experiences about their experience, awareness, intention, and barriers about smoking cessation and LDCT LCS. These in-depth interviews will last about 45 minutes and will be recorded for transcription. These findings will guide Objective 2. If the participant agrees to participate in the study, the research staff will then conduct the interview.

After the interview, the patient will be required to sign two sign in sheets to confirm he/she received the \$100 clinic card.

**Objective 2:** The proposed study will conduct a randomized clinical trial examining the effectiveness of a multiple levels intervention integrating lung cancer screening and smoking cessation (MILS) for African Americans undergoing LDCT. The developed MILS Intervention using the Theory of Planned Behavior and the Transtheoretical Model as a guiding framework, the content of the targeted smoking cessation intervention and LDCT uptake.

**Objective 3:** The research assistant (RA) will recruit/invite ten participants, 10 providers and 10 community members, to complete an in-depth interview after the MILS intervention. We will invite 10 intervention completers on the first complete first invited rule until data saturation is reached. This will result in a total of 30 participants for the interviews. Our team will schedule an interview time with the participants within one week after the participant fills out the post-intervention assessment. The interviews will be conducted through phone calls and will be audio-recorded. During the interviews, the interview facilitator will follow a semi-structured interview guide to ask participants to share their personal perspectives and experiences about the quality, usability, and user-friendliness about and experiences about barriers and facilitators that influence primary outcomes at the community, provider, and individual levels for the improvement of a multilevel intervention (MILS) to smoking cessation and LDCT LCS. Participants will also be asked to comment on why they are satisfied or unsatisfied with the MILS and the intervention and provide suggestions for intervention improvement and dissemination. These in-depth interviews will last about 45 minutes and will be recorded for transcription. After the interview, the patient will be required to sign two sign in sheets to confirm he/she get the \$100 clinic card.

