### **Research Objectives**

**Objective 1. Investigate smokers' and providers' attitudes, knowledge, and experiences with the expanded 2021 USPSTF Lung Cancer Screening (LCS) recommendations.** We will examine it using exploratory sequential mixed methods (integrating quantitative and Qualitative data). We will conduct focus groups for A.A. smokers who are eligible for LDC. Results will be used to expand the understanding of the needs and barriers of LDCT LCS and smoking cessation services to construct multiple levels intervention with the goal of increasing LDCT uptake and quitting behaviors.

**Objective 2. Compare the Effectiveness of a Multiple levels intervention integrating lung cancer screening and smoking cessation (MILS) vs. control group on the biochemically validated 7-day point-prevalence tobacco abstinence rates at 6 months, LDCT uptake, the change in tobacco consumption pattern, nicotine dependence and stage of change was assessed.** We will conduct a multiple level intervention integrating lung cancer screening and smoking cessation (MILS), including individual level: individual-based LDCT/smoking education (with Louisiana Tobacco Cessation Initiative); Institutional level: provider education (with university medical center); and community level: a community navigator (Community Health Worker) with interactive social media to increase LDCT uptake and quitting behaviors in racially and ethnically diverse populations. Multilevel intervention is a holistic approach to addressing health issues that recognize the complexity of health determinants. Multilevel interventions aim to change health behaviors and related outcomes by targeting multiple levels of influence, such as individuals, groups, organizations, and communities. Multilevel interventions can be delivered simultaneously or over time to achieve desired outcomes. For example, interventions integrating lung cancer screening and smoking cessation can work together synergistically to enhance early cancer detection and prevention.

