LDCT is an evidence-supported lung cancer screening that is noted to increase early-stage lung cancer diagnosis. Early diagnosis can reduce lung cancer-related mortality and improve prognosis. **For this study, we are not directly providing lung cancer screenings. We are recruiting participants who are eligible for lung cancer screening and increase their knowledge, attitude, and intention to take LDCT.** We hypothesize that A.A. in the MILS group will achieve greater increases in LDCT uptake and quitting behaviors (e.g., biochemically validated 7-day point-prevalence tobacco abstinence rates at 6 months, the change in tobacco consumption pattern, nicotine dependence and stage of change) at post-treatment and follow-up than A.A. in the control group.

**Objective 3. Explore barriers and facilitators that influence primary outcomes at the community, provider, and individual levels for the improvement of a multilevel intervention (MILS).** We will conduct 30 qualitative key informant interviews (10 for each level) to identify barriers and facilitators that influence the adherence and implementation of MILS.

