### **Study Questionnaires/ Assessment Tools**

Primary outcomes were measured by survey before intervention, immediately after intervention, and 6-month after intervention. Outcomes include stage of change, 7-day PPA rate, 24-hour PPA rate, daily cigarette use, and the Fagerstrom Test for Nicotine Dependence score. Stage of Change was measured based on the TTM model. 7-day PPA at follow-up was measured with the question "Have you smoked any tobacco products in the last 7 days?" 24-hour PPA was measured using the question "Have you smoked any tobacco products in the last 24 hours?" Daily cigarette use was measured using a multiple-choice question with 4 answers: 1) 10 or less, 2) 11-20; 3) 21-30; or 4) 31 or more. The Fagerstrom Test for Nicotine Dependence was based on a 6-item validated questionnaire (Etter et al., 1999) Second, the LDCT uptake and intent to LCS constructs were measured by previously validated questionnaires. An additional amendment will be submitted for Year 2 measurements and aims. All surveys and questionnaires will be submitted in an amendment for Year 2 of the study, including all intervention materials.

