### **Data Analysis**

**Objective 1:** Qualitative data collected from semi-structure interviews, which is a research method that combines a set of predetermined questions with the ability for the interviewer to explore specific themes or responses. These interviews allow for a mix of predetermined questions and others that are not based on the participant's responses. The interviews will be transcribed, de-identified, and enter into Atlas.ti for data analysis. A thematic analysis will be conducted to understand participants' perspectives on smoking cessation and LDCT LCS. The primary analysis will be performed by two researchers independently. These two researchers will review the first 5 interviews to open code the data and to identify emergent themes. The multidisciplinary research team will then have meetings to discuss, operationalize, and refine the codes and themes to develop a coding scheme. The two researchers will use the developed coding scheme to independently code all the transcripts. They will have regular meetings to review coded transcripts together, identify and reconcile any coding discrepancies, and add newly merged codes and themes into the coding scheme. We will calculate the code frequencies to identify the most frequently mentioned points by participants under each theme. The final coding results will be reviewed and shared with all research team members for feedback and revision.

**Objective 2:** We plan to enroll a total of 250 participants (125 for each group; experiment and control group). Assuming a 20% attrition rate, we estimated 200 (100 per group) participants at the end of the study at the 6-month follow-up visit. A significant level of 0.05 is applied. We estimated that the biochemically validated 7-day point-prevalence tobacco abstinence rates at 6 months are 20-30% for the MILS group and 5% for the control group (Martha Andritsou et al., 2016). A sample size of 200 achieves 85.6-99.6% power to detect the group difference in tobacco abstinence rates at 6 months based on the two-sided Fisher's exact test. For the LDCT uptake, we estimate that the LDCT uptake at 6 months is 32-40% for the MILS group and 15% for the control group (Young PC et al., 2020; Coral Olazagasti et al., 2022). A sample size of 200 achieves 76.5-97.2% power to detect the group difference of the LDCT update based on the two-sided Fisher's exact test (Ryan, 2013).

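### Objective 3 asks what hinders adherence to MILS, but its participant interviews are limited to people who completed it

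*Protocol*

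**What the plan says.** The Protocol's Research Objectives section gives Objective 3 two linked purposes. One is to "Explore barriers and facilitators that influence primary outcomes at the community, provider, and individual levels". The other is to hold 30 key informant interviews, ten per level, "to identify barriers and facilitators that influence the adherence and implementation of MILS".

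The Procedure section, under Objective 3, says that the research assistant "will recruit/invite ten participants, 10 providers and 10 community members, to complete an in-depth interview after the MILS intervention". It then fixes how the ten participants are found: "We will invite 10 intervention completers on the first complete first invited rule until data saturation is reached". Each is interviewed by telephone "within one week after the participant fills out the post-intervention assessment".

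The Study Sample/Recruitment section repeats the 10 + 10 + 10 split without mentioning completion, so the restriction rests on the Procedure section alone. Under Objective 3, the Data Analysis section adds feasibility records (recruitment, attrition, attendance, social media use) and a questionnaire on matters such as usefulness, burden and cultural sensitivity. No section provides for interviewing participants who left MILS or did not finish it.

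**The concern.** Completing the intervention is itself a form of adherence. A sample made up only of completers has little or no variation in what Objective 3 wants to understand. The people best placed to say why someone stopped, such as lack of transport or time, poor fit of the content or distrust, have no chance of being asked.

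What is at stake is how the results are used. Objective 3 is meant to improve MILS before dissemination. Themes drawn from completers alone are likely to favour what worked and to under-report what drove people away, and code frequencies from such a sample would make the programme look more acceptable than it was to the whole arm. The saturation clause does not help, because saturation among completers says nothing about themes held only by non-completers.

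**Working it through.** **1. The plan's own count.** 10 participants + 10 providers + 10 community members = 30, which is the total stated. The ten completers are therefore the whole of the individual-level sample, not an addition to it.

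**2. Purpose against rule.**

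| Item | Protocol section | Content |
|---|---|---|
| Purpose | Research Objectives, Objective 3 | What helps or hinders adherence, implementation and the primary outcomes |
| Who is asked, individual level | Procedure, Objective 3 | Completers of MILS, in order of completion |
| Other sources on non-adherence | Procedure; Data Analysis, Objective 3 | Providers and community members; attrition and attendance counts; questionnaire |

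Non-completers among the ten participant interviewees: 0, by construction.

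**3. What a sample blind to completion would contain.** The Data Analysis section states: "We plan to enroll a total of 250 participants (125 for each group; experiment and control group". The MILS arm is therefore 125. The only loss figure given is 20% attrition by the 6-month visit. It reproduces: 250 × 0.80 = 200, and 125 × 0.20 = 25 in the MILS arm. But it describes missing the 6-month visit, not failing to complete MILS, so it cannot be used as the non-completion rate. That rate is an assumption here, taken over a range.

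With m non-completers among 125 and ten people drawn at random:
- expected number = 10 × m / 125
- P(at least one) = 1 − C(125 − m, 10) / C(125, 10)

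| Assumed non-completion | m (rounded up) | Expected among 10 | P(at least one) |
|---|---|---|---|
| 10% | 13 | 1.0 | 68% |
| 20% | 25 | 2.0 | 90% |
| 30% | 38 | 3.0 | 98% |

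So the rule takes the expected number from about 1-3 to 0.

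**4. What completers can still report.** The Data Analysis section assumes 6-month abstinence of 20-30% and LDCT uptake of 32-40% in the MILS arm. If completers resemble the arm as a whole, then of ten:
- not abstinent: 10 × (1 − 0.30) = 7 to 10 × (1 − 0.20) = 8
- not screened: 10 × (1 − 0.40) = 6.0 to 10 × (1 − 0.32) = 6.8

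Most interviewees could therefore speak about obstacles to quitting or screening. The gap is specific to non-adherence.

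**5. Timing.** Surveys are taken "before intervention, immediately after intervention, and 6-month after intervention", and the Project Timeline lists the post-intervention and 6-month assessments as separate activities. The interview is therefore read as following the immediate assessment and preceding the "biochemically validated 7-day point-prevalence tobacco abstinence rates at 6 months". Participants cannot be chosen by 6-month outcome. However, the survey immediately after the intervention is available, and questionnaires carry participant ID numbers (Protection of Privacy section). Nothing in the Protocol prevents transcripts from being grouped by 6-month status at analysis.

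**The case against.** The best defence is that Objective 3 is exploratory and draws on more than these ten people. Twenty of the 30 interviews are with providers and community members, who can describe obstacles at their own levels. Attendance and attrition are recorded, and a questionnaire covers burden. The interview guide asks about quality, usability and satisfaction, which requires exposure to MILS. No efficacy estimate rests on the interviews.

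All of that is true, and it limits the point. It does not answer it. Providers and community members can only report second-hand why a participant disengaged, and counts show how many, not why. Partial exposure is enough to say why one stopped.

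A reader might infer several stronger things that the documents do not support:

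- *That Objective 3 cannot show what stops people quitting or being screened.* Completing MILS is neither of these, and most completers are expected to be non-abstinent or unscreened at 6 months.
- *That people lost to follow-up are excluded by rule.* A completer who is later lost before 6 months remains eligible.
- *That 25 of 125 measures who is shut out.* That is 6-month attrition, a different quantity.
- *That the sample is the fastest completers.* The rule follows calendar order, which under staggered enrolment may only reflect early entry.
- *That the interview and its $100 card distort the 6-month comparison.* At most 10/125 = 8% of the arm is interviewed. Even if the interview raised abstinence by an assumed 10 percentage points in every interviewee, the arm rate would move by 0.08 × 10 = 0.8 points, against a planned difference of 15 to 25 points (20 − 5 to 30 − 5).
- *That the interviews must move to after the 6-month visit.* That would lengthen recall and lose those who drop out in between. It is a trade-off, not a correction.

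**Conclusion.** The point holds in a limited form. The stated purpose includes explaining adherence to MILS, while the sampling rule removes from the individual-level interviews everyone who did not complete it, and no other part of the Protocol supplies their first-hand account. The loss is total for that group. The figure of about 1 to 3 missed voices in ten depends on an assumed non-completion rate of 10-30% and on a random draw as the comparison. The Protocol does not define a completer, so whether low attenders are also excluded depends on how the term is applied. The randomised comparison, its sample size and its power are untouched. Barriers to quitting and screening remain partly within reach, and the planned timing is acceptable.

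**What to change.** In the Procedure section, Objective 3, replace the completer rule with purposive sampling from all participants assigned to MILS. Keep ten participant interviews and reserve some of the places for non-completers or low attenders. The documents do not determine how many, so the study team should set and state the number. Say what counts as completing MILS.

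A non-completer may never fill out the post-intervention assessment, so tie contact with that group to the date the assessment is due. For completers the one-week window can stay. Add a short set of questions on why participation stopped, and plan to group transcripts by 6-month abstinence and LDCT status once these are known.

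The cost is a wording change and a small addition to the interview guide. The number of interviews and the payment stay the same. The downsides are that non-completers are harder to reach, so some reserved places may need several attempts, and that fewer completers are heard.

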### **Data Collection Methods**

Quantitative surveys will be distributed to survey participants. All qualitative interviews will be conducted via Zoom and analyzed with Atlas.ti software. Atlas.ti software is compliant with HIPAA, FERPA, and meets ADA compliances and will be encrypted on LSUHSC computers.

### **Data Management**

To safeguard confidentiality, all data is maintained in an electronic form that can only be accessed by the study personnel. The information obtained throughout the experimental study will be stored electronically using password-protected computers on encrypted drives.

### **Data Analysis**

**Objective 1:** Qualitative data collected from semi-structure interviews, which is a research method that combines a set of predetermined questions with the ability for the interviewer to explore specific themes or responses. These interviews allow for a mix of predetermined questions and others that are not based on the participant's responses. The interviews will be transcribed, de-identified, and enter into Atlas.ti for data analysis. A thematic analysis will be conducted to understand participants' perspectives on smoking cessation and LDCT LCS. The primary analysis will be performed by two researchers independently. These two researchers will review the first 5 interviews to open code the data and to identify emergent themes. The multidisciplinary research team will then have meetings to discuss, operationalize, and refine the codes and themes to develop a coding scheme. The two researchers will use the developed coding scheme to independently code all the transcripts. They will have regular meetings to review coded transcripts together, identify and reconcile any coding discrepancies, and add newly merged codes and themes into the coding scheme. We will calculate the code frequencies to identify the most frequently mentioned points by participants under each theme. The final coding results will be reviewed and shared with all research team members for feedback and revision.

**Objective 2:** We plan to enroll a total of 250 participants (125 for each group; experiment and control group). Assuming a 20% attrition rate, we estimated 200 (100 per group) participants at the end of the study at the 6-month follow-up visit. A significant level of 0.05 is applied. We estimated that the biochemically validated 7-day point-prevalence tobacco abstinence rates at 6 months are 20-30% for the MILS group and 5% for the control group (Martha Andritsou et al., 2016). A sample size of 200 achieves 85.6-99.6% power to detect the group difference in tobacco abstinence rates at 6 months based on the two-sided Fisher's exact test. For the LDCT uptake, we estimate that the LDCT uptake at 6 months is 32-40% for the MILS group and 15% for the control group (Young PC et al., 2020; Coral Olazagasti et al., 2022). A sample size of 200 achieves 76.5-97.2% power to detect the group difference of the LDCT update based on the two-sided Fisher's exact test (Ryan, 2013).

**Objective 3:** Feasibility (e.g., recruitment rates, attrition rates, attendance rate, register and use social media) will be documented. The questionnaire will assess the intervention's overall usefulness, content/context, interest, burden, cultural sensitivity. Satisfactory measurements were conducted during the process evaluation using a short survey. All questionnaires concerning feasibility, intervention usefulness, content/context, interest, burden, cultural sensitivity, and satisfactory measurements will be distributed during the follow-up period of the intervention. Thus, these documents will be submitted in an amendment at a later date once the process evaluation is completed.

Qualitative data collected from semi-structure interviews will be transcribed, de-identified, and enter into Atlas.ti for data analysis. A thematic analysis will be conducted to understand participants' perspectives on smoking cessation and LDCT LCS. The primary analysis will be performed by two researchers independently. These two researchers will review the first 5 interviews to open code the data and to identify emergent themes. The multidisciplinary research team will then have meetings to discuss, operationalize, and refine the codes and themes to develop a coding scheme. The two researchers will use the developed coding

scheme to independently code all the transcripts. They will have regular meetings to review coded transcripts together, identify and reconcile any coding discrepancies, and add newly merged codes and themes into the coding scheme. We will calculate the code frequencies to identify the most frequently mentioned points by participants under each theme. The final coding results will be reviewed and shared with all research team members for feedback and revision.

